#### *Analysis of Efficacy of Omegaven®*

The primary outcome to gain preliminary evidence of efficacy will be based on the time from baseline to normalization of bilirubin level, i.e., first time point among three consecutive in which bilirubin is < 2 mg/dL. We do not anticipate that any subject will present a rebound on direct bilirubin after normalization. However, we will describe the cohort with respect to the frequency of rebounds in bilirubin levels.

Time to normalize direct bilirubin levels will be estimated using Kaplan-Meier curves. We will estimate hazard ratios and adjust for potential baseline confounders using Cox-proportional hazard models. For all survival analysis based on non-parametric or semi-parametric methods, we will attribute an infinite time to event for subjects who die or receive a liver transplant before bilirubin is normalized. Subjects who die before their bilirubin levels normalize (particularly due to liver failure) have in fact the worst outcome (infinite time to normalize bilirubin) and were not censored before reaching the endpoint of interest. Results of these analyses will be compared with results of analysis excluding subjects who die or are transplanted. Time to reach a total bilirubin of 1.2 will also be estimated using survival analysis methods. Analyses of this outcome will proceed as described for direct bilirubin.

We will also describe individual profiles over time (i.e., 2 months before baseline or birth until end of follow-up period) for all subjects using graphical methods. Trends in liver function markers over time will be explored using generalized linear models in which correlations of observations within subjects will be accounted using a generalized equations or random effects approach. We will perform these analyses including only subjects who did not die or undergo transplantation and including all subjects but assigning for subjects who died or underwent a transplant their worse possible outcome after they died or had the transplant. Using descriptive statistics, we will also explore the association between spikes in blood tests over time and predictors including transfusions of red blood cell products and blood stream infections.

Assessment of efficacy will be also based on comparison of means (or medians) of the mean and maximum modified PELD scores of each subject across all follow-up weeks. Adjustments of these comparisons for potential confounders will be based on linear regression models. Mean rates of infection will be compared using logrank and Cox proportional hazards models.

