**Hypothesis for Aim 2:**

2.1 – Our primary hypothesis is that, after reaching bilirubin levels  $> 2$  mg/dL, patients receiving Omegaven® will reach a bilirubin level  $\leq 2$  mg/dL faster than patients receiving conventional fat emulsions. Additionally, while patients receiving Omegaven® will experience a decrease in their levels of bilirubin and other hepatic enzymes over time, patients receiving conventional emulsions will maintain high levels of bilirubin and other hepatic enzymes over time.

2.2 – Patients with surgical gastrointestinal disease and cholestasis will have better clinical hepatic outcomes than patients receiving conventional emulsions.

2.3 – Since patients receiving Omegaven® will have improved immune function, they will have a lower infection rate than patients receiving conventional fat emulsions.

2.4 – Due to a better general hepatic condition, patients receiving Omegaven® will also experience lower occurrence of liver transplant, death from hepatic associated causes, and blood transfusions.

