**Inclusion Criteria:**

1. Patients will be PN dependent (unable to meet nutritional needs solely by enteral nutrition) and are expected to require PN for at least another 30 days.
2. Patients considered eligible for study participation must have parenteral nutrition associated liver disease (PNALD) as defined as a direct bilirubin of  $\geq 2$  mg/dl on at least the last two consecutive measures or by histology and/or currently on Omegaven through another protocol and unable to remain on that protocol due to transfer to our institution. Other causes of liver disease should be excluded. A liver biopsy is not necessary for treatment.
3. The patient must have utilized standard therapies to prevent the progression of his/her liver disease including surgical treatment, cyclic PN, avoiding overfeeding, reduction/removal of copper and manganese from PN, advancement of enteral feeding, and the use of ursodiol (i.e., Actigall®).
4. Patients ages birth up to and including 18 years of age.

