### Resumption of Therapy

For patients who have been off the protocol more than 1 year, in the event that the patient must receive intravenous fat emulsion, treatment with Omegaven® will resume only if the patient shows evidence of PN liver damage (elevations in direct bilirubin  $\geq 2$  or pathology findings consistent with cholestasis). Otherwise, the patient will be treated with conventional fat emulsion.

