### **D. Definition of Primary and Secondary Outcomes/Endpoints**

Generally, primary safety analyses will be based on time from baseline or 30 days after baseline until two months after patients first reached direct bilirubin levels  $< 2$  mg/dL. Baseline will be defined as information collected at the date that treatment starts for Omegaven® patients and on the date that patient reached bilirubin levels  $> 2$  for soybean oil fat emulsion patients. Information on mortality and transplant will be collected during the whole treatment with Omegaven®. Primary efficacy analysis will include time from baseline until the patient normalizes bilirubin (presents three consecutive direct bilirubin  $\leq 2$  mg/dL or a direct bilirubin  $\leq 2$  mg/dL and weaned from TPN).

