### *Analysis of Baseline Characteristics*

For statistical purposes, baseline values will be defined as the last measurement before starting to administer Omegaven®. Descriptive statistics for all baseline relevant risk factors will be summarized using counts and percentages for categorical variables and means (and standard deviations) or medians (and interquartile ranges), when appropriate for continuous variables.

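### The protocol defines the primary efficacy event in two ways: direct bilirubin at or below 2 mg/dL with a weaning route, and below 2 mg/dL without one

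*Protocol*

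**What the plan says.** **Event, section D (Definition of Primary and Secondary Outcomes/Endpoints).** "Primary efficacy analysis will include time from baseline until the patient normalizes bilirubin (presents three consecutive direct bilirubin" values of at most 2 mg/dL. The same sentence gives a second route: a single direct bilirubin of at most 2 "mg/dL and weaned from TPN".

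**Event, Analysis of Efficacy of Omegaven®.** The primary outcome is time from baseline to normalisation, spelled out as the "first time point among three consecutive in which bilirubin is < 2 mg/dL". Weaning is not mentioned.

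**Hypothesis 2.1.** "Our primary hypothesis is that, after reaching bilirubin levels" above 2 mg/dL, Omegaven patients will come down to ≤ 2 sooner than patients on conventional emulsions.

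**Disease threshold.** Inclusion criterion 2 asks for direct bilirubin ≥ 2 on at least the last two measures, but also admits patients "or by histology and/or currently on Omegaven through another protocol and unable to remain on that protocol due to transfer to our institution". Under Resumption of Therapy, Omegaven "will resume only if the patient shows evidence of PN liver damage (elevations in direct bilirubin" of 2 or more, or pathology findings). The Reversal Study Lab Schedule splits its rows at ≥ 2 and < 2.

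**Time zero.** "Baseline will be defined as information collected at the date that treatment starts for Omegaven® patients". For soybean oil patients it is the date on which bilirubin exceeded 2. Analysis of Baseline Characteristics adds that "baseline values will be defined as the last measurement before starting to administer Omegaven".

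**The concern.** Section D and Analysis of Efficacy describe the same primary efficacy outcome but differ on the threshold (≤ 2 or < 2) and on whether weaning with one low value counts. The analysis section offers its wording as the definition, so it cannot be read as shorthand for section D. Hypothesis 2.1 sides with section D on the threshold, and no sentence sets an order of precedence. Two analysts following the text could code the same child differently. If the rule were chosen after the data are seen, it could be chosen for its answer.

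The weaning route is the more important difference. Weaning from PN is the planned end of treatment (Duration of Therapy), and the minimum lab schedule does not secure three low values by then.

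A secondary point concerns who enters the analysis. The histology and transfer routes carry no bilirubin floor, and the clock starts at treatment start whatever the bilirubin. A patient already at or below the threshold has no elevation to reverse, yet can be counted as normalised at or near time zero.

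**Working it through.** The protocol gives no figure for the efficacy endpoint, so there is nothing to reproduce. Table 4 covers McNemar safety comparisons only.

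**1. The rules side by side**

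| | Section D | Analysis of Efficacy | Hypothesis 2.1 |
|---|---|---|---|
| Threshold | ≤ 2 | < 2 | ≤ 2 |
| Three consecutive values | yes | yes | not stated |
| One value plus weaning | yes | no | not stated |
| Value that dates the event | not stated | first of the three | not stated |

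A value of exactly 2.0 is normalised under section D, not normalised under Analysis of Efficacy, and still disease under the inclusion and resumption criteria.

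**2. Both rules applied to invented weekly series** (assumed values; week 0 is baseline; events dated at the first qualifying value)

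| Series | Section D | Analysis of Efficacy |
|---|---|---|
| 4, 3, 2.0, 2.0, 2.0, 1.8, 1.6, 1.5 | week 2 | week 5 |
| 4, 3.2, 2.6, 2.2, 1.8, weaned at week 4, no later labs | week 4 | no event |
| Entry at 2.0: 2.0, 2.0, 2.0, 2.0, 1.9, 1.8, 1.7 | week 0 | week 4 |
| Histology entry: 1.5, 1.4, 1.2, 1.0 | week 0 | week 0 |
| Transfer on Omegaven: 0.8, 0.7, 0.6, 0.6 | week 0 | week 0 |

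The first three rows show the conflict; the last three show the entry gap. If the baseline value is not counted, the week 0 events move to the first later measurement at the earliest.

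**3. Can a weaned child have fewer than three low values?** Let d be the days from the first low value to stopping Omegaven, and count scheduled values from the Reversal Study Lab Schedule.

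- Outpatient, monthly draws below 2, which may end once off Omegaven with one value < 2: 1 + floor(d/30). This gives 1 for d < 30, 2 for d = 30 to 59, and 3 from d = 60.
- Inpatient, weekly PN profile below 2 plus one complete set after Omegaven: 1 + floor(d/7) + 1. This gives 2 for d < 7 and at least 3 from d = 7. It assumes that the PN profile includes direct bilirubin; its contents are not listed.

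So it is possible, mainly for outpatients. Missing Values interpolates only gaps in the middle of follow-up, so it cannot supply values after the last draw. These counts are scheduled minimums and are tied to stopping Omegaven. Section D's route turns on weaning from TPN, and Duration of Therapy lets Omegaven continue after the dextrose/protein portion stops, so the two dates can differ.

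**4. Size per child.** At the cohort sizes in Statistical Power and Sample Considerations: 1/20 = 5.0, 1/25 = 4.0 and 1/30 = 3.3 percentage points of the cohort.

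**5. Direction.** If both rules date at the first low value, section D's event is never later, because its conditions are weaker. Section D does not state that dating. Take 4, 3, 1.8, 1.6, 1.5: Analysis of Efficacy gives week 2, while section D read as the time the third value is seen gives week 4. The order has reversed. On monthly draws the gap would be about 2 × 30 = 60 days.

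**The case against.** The best defence is that little rests on this endpoint. Efficacy is called preliminary, the sample size is not based on power, and no decision rule is attached. That stands, and it limits the consequences. It does not remove the contradiction: a SAP that picked one rule would still conflict with one section of the protocol.

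Three stronger readings are tempting, and the documents do not support them.

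- *A reader might infer that the plan necessarily yields two different results.* Results differ only if some child has a deciding value of exactly 2.0 or is weaned with fewer than three low values. The protocol gives no frequency for either. Draws beyond the minimum are allowed, and follow-up runs at least 2 months after stopping (Discontinuation of Therapy), although that section names no labs.
- *A reader might infer that section D always gives the faster, more favourable answer.* That needs first-value dating under both rules, which section D does not state; step 5 shows the order reversing.
- *A reader might infer a sizeable bias in the median from patients who enter already below the threshold.* The mechanism is real, but the protocol gives no numbers by entry route, so no size can be attached.

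It can also be said that Hypothesis 2.1 already assumes a start above 2, and that the choice of analysis set is often left to a SAP. In part this is fair, which is why entry is secondary here. However, section D's operative baseline applies the > 2 condition only to soybean oil patients, so the hypothesis wording does not close the gap.

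**Conclusion.** The point holds as a conflict between two sections over the primary efficacy event, in threshold and in weaning route, with no statement of which governs. The lab schedule makes the weaning conflict a practical possibility. Each reclassified child is 3.3 to 5.0 percentage points of a cohort of 30 to 20. This is a share of patients, not a shift in the Kaplan-Meier estimate that the plan will report. The number affected cannot be derived from the protocol, and the direction is known only under common first-value dating.

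The entry gap also holds, as a secondary point of unknown size. For transferred patients it is unclear whether treatment start means the start here or at the earlier institution. If it means the earlier one, their events need not lie near time zero.

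**What to change.** 1. **One definition** in Hypothesis 2.1, section D and Analysis of Efficacy, with one threshold used for both baseline and event in both patient groups. Either option resolves the conflict:
   - event < 2 with baseline ≥ 2. This complements the ≥ 2 in the inclusion and resumption criteria and matches the lab schedule's cut-point. It changes the wording of Hypothesis 2.1 and the > 2 baseline for soybean oil patients.
   - event ≤ 2 with baseline > 2. This changes Analysis of Efficacy and places patients who enter at exactly 2.0 outside the time-to-event set.
2. **Dating.** Date the three-value route at the first of three consecutive post-baseline values. Keep the weaning route, dated at the first value of the final uninterrupted run of post-baseline values meeting the threshold up to weaning. For 4, 1.8, 2.4, 1.9, then weaned, the date is that of the 1.9, so the rebound to 2.4 is not ignored.
3. **Sensitivity analysis** requiring three consecutive values.
4. **Analysis set.** Restrict time to normalisation to patients who do not yet meet the event threshold at the last measurement before the first Omegaven infusion. Describe the others separately, including those transferred on Omegaven, and state which institution's start counts as treatment start.

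The cost is wording in three sections, one analysis-set rule and one sensitivity analysis. No extra blood draws are needed, and eligibility and treatment rules are untouched. The downside is a slightly smaller efficacy set and a possibly less favourable estimate.

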### Outcome/Endpoints

#### *Treatment safety*

Our primary outcome for treatment safety will be based on patient's essential fatty acid profile. We will compare patients before treatment with Omegaven® started and after treatment started (one month after treatment started until treatment stopped) with respect to the frequency with which triene/tetraene ratio  $> 0.2$  at any time. Primary analyses for these and all other safety outcomes will be based on a follow-up time for Omegaven® starting 30 days after baseline, i.e., 30 days after treatment started for Omegaven® patients and 2 months after the first direct bilirubin level  $< 2$  mg/dL was recorded.

Additional comparisons across treatment periods for subjects receiving Omegaven® will be aimed to assess occurrence of spontaneous bleeding (e.g., unexplained bruising, oozing from gums/incision sites), and maximum triene/tetraene ratio, minimum platelets, maximum international normalized ratio (INR), and trends in pre-albumin (age standardized levels). We will also explore trends in coagulopathies based on curves of platelets, prothrombin time (PT), partial thromboplastin time (PTT) over time, and INR. We will also describe the rate with which INR ratios were  $> 2$  (number of days/follow-up time), as a marker of coagulopathies.

Additional evaluation of Omegaven® will be performed with regards to rate in which albumin is  $> 3$  g/dL, maximum triglyceride level, rate of blood stream infections (number of positive blood cultures/follow-up-time under PN after baseline), rate of central venous catheter (CVC) infections (number of CVC infections/follow-up time and number of gram positive CVC infections/follow-up time), and occurrence of anaphylactic reactions after baseline.

We will describe trends over time for all outcomes associated with fatty acid profiles (including triene/tetraene ratios, triglycerides, total omega-6 fatty acids, total omega-3 fatty acids, total saturated, total monounsaturated, and total polysaturated fatty acids). Specific fatty acids such as arachidonic, palmoleic, palmitic, oleic, stearic, and linoleic fatty acids will also be evaluated and described.

[name], Department of Surgery, Children's Hospital & Medical Center  
[name], Department of Surgery, Children's Hospital & Medical Center  
[name], Pediatric Research Office, Dept. of Pediatrics, UNMC  
[name], Department of Biostatistics, College of Public Health, UNMC

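### The infinite-time rule for death and transplant is worded for all survival analyses but suits only the bilirubin endpoints; applied to the logrank/Cox infection analysis it would understate the infection hazard

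*Protocol*

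**What the plan says.** All but two of the relevant statements stand in the protocol's Data Analysis Plan, under Analysis of Efficacy of Omegaven®.

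- **The rule.** After naming Kaplan-Meier and Cox methods for time to normalize direct bilirubin, the section states "For all survival analysis based on non-parametric or semi-parametric methods, we will attribute an infinite time to event for subjects who die or receive" and completes the sentence with "a liver transplant before bilirubin is normalized".
- **Its reason.** Children who die before normalization "have in fact the worst outcome (infinite time to normalize bilirubin) and were not censored before reaching the endpoint of interest".
- **A check.** "Results of these analyses will be compared with results of analysis excluding subjects who die or are transplanted".
- **A second endpoint.** For time to a total bilirubin of 1.2: "Analyses of this outcome will proceed as described for direct bilirubin".
- **Infection.** At the end of the section: "Mean rates of infection will be compared using logrank and Cox proportional hazards models". Nothing is said there about death or transplant.

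Elsewhere, the Treatment safety outcomes define a separate infection measure, the "rate of blood stream infections (number of positive blood cultures/follow-up-time under PN after baseline", and Hypothesis 2.3 expects that patients on Omegaven® "they will have a lower infection rate than patients receiving conventional fat emulsions".

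**The concern.** The logrank test is non-parametric and the Cox model is semi-parametric, so the infection analysis falls within the rule's stated scope. No other sentence tells the analyst what to do there with a child who dies or is transplanted.

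The reasoning behind the rule does not carry over. Normalization is a desirable event, so never reaching it is the worst result. Infection is an undesirable event, so never reaching it is the best result. A child who dies uninfected before normalization would stay in the infection risk set, infection-free, to the end of follow-up. The trigger is also unrelated to infection: two children who die uninfected on the same day would be handled differently according to whether bilirubin had normalized. For transplant, the rule would credit infection-free time after the point at which the protocol's withdrawal criteria (item c) take the child off study.

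At stake is the hazard on which the logrank/Cox assessment of Hypothesis 2.3 rests.

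**Working it through.** **Figures in the documents.** The protocol gives no infection rate and no death or transplant proportion, so there is no figure of its own to reproduce. The inputs below are assumptions, shown over a range.

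**Assumptions.** One common follow-up period of length 1. Constant, independent hazards of infection (λ) and of death or transplant (μ). All deaths and transplants occur before normalization.
- p = proportion infected by the end if nobody died or was transplanted: 30% or 50%. λ = −ln(1 − p).
- q = proportion who die or are transplanted by the end: 5%, 10%, 20% or 30%. μ = −ln(1 − q).
- s = λ + μ.

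The rate (events over person-time) stands in for the hazard that logrank and Cox work with.

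**Formulas.**
- Infections before death or transplant: E = (λ/s)(1 − e^(−s)).
- Person-time if follow-up ends at death or transplant: T₁ = (1 − e^(−s))/s. Then E/T₁ = λ, so the estimate is correct.
- Person-time under the rule, with uninfected deaths and transplants kept at risk to the end: T₂ = λ[1 − e^(−s)(1 + s)]/s² + (1 − E).
- Estimate relative to truth: (E/T₂)/λ.

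**Worked case, p = 30%, q = 20%.**
- λ = 0.357, μ = 0.223, s = 0.580, e^(−s) = 0.7 × 0.8 = 0.56.
- E = (0.357/0.580) × 0.44 = 0.271.
- T₁ = 0.44/0.580 = 0.759, and 0.271/0.759 = 0.357 = λ.
- T₂ = 0.122 + 0.729 = 0.852, and 0.271/0.852 = 0.318.
- Ratio: 0.318/0.357 = 0.89, an understatement of 11%.

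**Estimated over true infection hazard under the rule.**

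| Die or transplanted (q) | p = 30% | p = 50% |
|---|---|---|
| 5% | 0.973 | 0.972 |
| 10% | 0.946 | 0.944 |
| 20% | 0.891 | 0.886 |
| 30% | 0.834 | 0.827 |

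The understatement therefore runs from about 3% to about 17%.

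**What is not affected.** In the worked case the proportion infected at the end of follow-up is 0.271 under the rule, against 0.30 from a curve that censors at death. The 0.271 is the true cumulative incidence with death or transplant as a competing event, so it is not a bias. The bloodstream infection rate in the Treatment safety outcomes divides by time under PN. A child who has died adds none, so that rate does not change.

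**Between groups.** If both groups had the same p and q, the factors would cancel. With p = 30%, no true difference, and 10% against 30% dying or transplanted, the apparent ratio of hazards would be 0.946/0.834 = 1.13 or its inverse 0.88, depending on which group has more deaths and transplants.

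**The case against.** The strongest reply is that this is a bilirubin rule, loosely introduced. Much of that stands:

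- The rule follows directly on the Kaplan-Meier and Cox analysis of direct bilirubin, and its sentence ends with a bilirubin condition.
- Its reason speaks only of time to normalize bilirubin.
- The method is then extended by name to total bilirubin, which would be needless if it already governed every survival analysis.
- For trends in liver markers, one of the two planned analyses gives children who die or are transplanted their worst outcome. Scoring death as infection-free would run against that principle.

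A reader might therefore infer too much by saying that the plan does score death as never infected. The infection sentence does not invoke the rule. What remains is that the scope words say otherwise and no competing instruction exists.

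A reader might also infer a bias against Omegaven® from Hypothesis 2.4, which expects fewer deaths and transplants on that product. That is a hypothesis under study. The documents give no such rates by group, so the direction is open.

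The planned comparison with an analysis excluding children who die or are transplanted does not settle the matter. It selects children on a future event and discards their infections and their genuine time at risk.

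Finally, detailed handling of competing events for a secondary endpoint may be left to a statistical analysis plan. That is fair, and its absence is not the point here. The point is a rule that the protocol does state, with a scope wider than its reason.

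**Conclusion.** The point holds as a defect of scope. Applied as written to the logrank/Cox infection analysis, the rule would understate the infection hazard by roughly 3% to 17% when 5% to 30% of children die or are transplanted before normalization. This rests on assumed proportions, constant independent hazards and a common follow-up, and on the reading that an infection recorded before death still counts. On the harsher literal reading, in which every such child is given infinite time even after an infection, the same assumptions give ratios of 0.941 down to 0.627, an understatement of about 6% to 37%. On that reading the cumulative incidence would also fall, to 0.24 in the worked case. The documents do not call for that reading, and I do not rest the point on it.

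The documents do not show that infection results will be biased, and the bilirubin analyses are not in question. The matter is minor: infection is a non-primary analysis in a study that seeks only preliminary evidence of efficacy.

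**What to change.** Make two edits under Analysis of Efficacy of Omegaven®:

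1. Replace the opening scope phrase of the infinite-time sentence with: *For the analyses of time to direct and total bilirubin normalization*.
2. After the infection sentence, add: *In the logrank and Cox analyses of infection, follow-up ends at death or transplant.*

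The cost is two sentences. No new data are needed, and the bilirubin analyses and the count-based infection rates do not change.

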#### **F. Study Timeline**

This study will end when the results of an FDA approved clinical trial proves Omegaven® treatment to be ineffective, the product is approved for use in the United States, or funding mechanism no longer exists to supply Omegaven® to study participants.

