**Patients will be withdrawn from the study for any of the following:**

- a) Toxicity considered unacceptable by the Principal Investigator (i.e. Evidence of burr cell anemia (reported toxicity); Continued lipid intolerance (triglyceride >200) despite dose reduction attempts and administration modification; evidence of coagulopathy (INR > 2.0)).
- b) Patient/guardian requests to discontinue treatment and/or observation for any reason.
- c) A suitable organ has been located and the patient is able to undergo a liver or liver/intestinal transplant.
- d) Decision by the Principal Investigator that termination is in the patient's best medical interest.
- e) Patient is lost to follow up.

In the event that a patient is withdrawn from the protocol, study staff will document the date of withdrawal, the reason for withdrawal, and the results of all measurements of interest made up to date of withdrawal.

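### Giving children who die or are transplanted an infinite event time biases the Kaplan-Meier normalisation curve slightly downward once other children are censored early; a competing-risks estimator avoids this

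*Protocol*

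**What the plan says.** Protocol, Analysis of Efficacy of Omegaven®, takes time from baseline to normalisation of bilirubin as the primary efficacy outcome.

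- Curve: "Time to normalize direct bilirubin levels will be estimated using Kaplan-Meier curves".
- Regression: "We will estimate hazard ratios and adjust for potential baseline confounders using Cox-proportional hazard models".
- Death or transplant first: "we will attribute an infinite time to event for subjects who die or receive a liver transplant before bilirubin is normalized". The reason given is that children who die before normalising have the worst outcome and "were not censored before reaching the endpoint of interest".
- Only check: "Results of these analyses will be compared with results of analysis excluding subjects who die or are transplanted".
- The same approach applies to time to a total bilirubin of 1.2.

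Other sections allow living children to leave observation before they normalise.

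- F. Study Timeline ties closure to outside events: "This study will end when the results of an FDA approved clinical trial proves Omegaven® treatment to be ineffective", or US approval, or the end of funding.
- The withdrawal list includes "Patient/guardian requests to discontinue treatment and/or observation for any reason" and "Patient is lost to follow up", besides toxicity and investigator decision.

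The section names no competing-risks estimator and no censoring weight. It sets no point at which a child given infinite time leaves the risk set.

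**The concern.** The intended quantity is the probability of having normalised by time t, with death or transplant counted as never normalising. Kaplan-Meier with infinite times estimates this exactly when every other child is followed to the horizon. When some are censored earlier, the risk set becomes unbalanced. Living children drop out at the censoring rate, while children who died or were transplanted never do. Later risk sets then hold too many children who cannot have the event, the estimated hazard of normalisation is too low, and the curve ends too low.

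At stake is the primary efficacy curve and its median. The size of the error depends partly on when an outside event closes the study. The protocol itself fixes the rule, so this is not a detail left to a later analysis plan.

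**Working it through.** **Inputs.** The protocol gives no rate of normalisation, death, transplant or censoring, so it has no figure of its own to reproduce. It gives the estimator, the infinite-time rule, the routes to censoring, and sample sizes of 20, 25 and 30 (Statistical Power and Sample Considerations). All rates below are assumptions, shown as ranges.

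**1. Constant hazards over a horizon scaled to 1.** Let h1 be the hazard of normalisation, h2 of death or transplant, g of censoring, and a = h1 + h2 + g. In large samples the infinite-time method estimates the hazard

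h1·e^(−at) / [e^(−at) + b(1 − e^(−at))], with b = h2/a.

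Integrating to the horizon gives 1 − KM = 1 − D^k, where D = b + (1 − b)e^(−a) and k = h1/[a(1 − b)].

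Take true normalisation 60% and death or transplant 20%. Then h1 + h2 = −ln(0.2) = 1.609, h1 = 0.75 × 1.609 = 1.207 and h2 = 0.402.

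- No censoring: a = 1.609, b = 0.25, D = 0.25 + 0.75 × 0.2 = 0.40, k = 1. So 1 − KM = 0.60, which is exact.
- 30% censoring: g = −ln(0.7) = 0.357, a = 1.966, b = 0.2046, D = 0.2046 + 0.7954 × 0.14 = 0.316, k = 0.772. So 1 − KM = 1 − 0.316^0.772 = 0.589, which is 1.1 points low.

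Bias in points, for a true 60%:

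| Death/transplant | 20% censored | 30% | 50% | 70% |
|---|---|---|---|---|
| 10% | −0.4 | −0.6 | −1.2 | −2.3 |
| 20% | −0.7 | −1.1 | −2.2 | −4.1 |
| 30% | −0.9 | −1.5 | −3.0 | −5.2 |

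**2. Timing of events.** At about 20 to 30% censoring, varying the timing gives about −0.2 (early normalisation, late deaths) to −2.6 (early deaths, late normalisation). Early deaths with 50% censoring give −3.3, −5.1 and −6.1 at 10%, 20% and 30% death or transplant.

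**3. Calendar-type censoring.** Monthly hazards are 0.15 to 0.25 for normalisation and 0.03 to 0.10 for death or transplant. The same hazard formula is used with uniform censoring. Understatement in points:

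| Censoring spread over | 6 months | 9 months | 11 months |
|---|---|---|---|
| 3–24 months | 0.2–0.5 | 0.9–1.2 | 1.5–1.8 |
| 0–24 months | 0.4–1.1 | 1.2–2.0 | 1.8–2.5 |
| 0–12 months | 1.1–2.6 | 3.5–4.8 | 5.9–6.9 |

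The last row needs care. With hazards 0.15 and 0.06, the number out of 30 still alive, uncensored and not normalised is 30 × e^(−0.21t) × (1 − t/12). That is 4.3 at 6 months, 1.1 at 9 and 0.25 at 11. The largest figures therefore describe a tail with almost nobody at risk.

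**4. At trial size.** With n = 30, hazards 0.15 and 0.06 and censoring over 0–12 months, the true value at 9 months is (0.15/0.21)(1 − e^(−1.89)) = 0.606. Simulated means are 0.559 by the stated method and about 0.602 by Aalen-Johansen. Root-mean-square error is 0.119 against 0.120 at 9 months, and 0.107 against 0.109 at 6. Across the n = 20 to 30 scenarios with a true 60%, Aalen-Johansen averages 59.6% to 60.4%, and the SD of the estimate is 9 to 13 points.

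**5. Cox.** Hazard ratios for two hypothetical groups, infinite times against risk time ended at potential censoring:

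- Equal censoring: 1.689 v 1.661 (+1.7%), 1.802 v 1.766 (+2.0%), and under no effect 0.978 v 0.980 (−0.2%).
- Unequal censoring: 1.695 v 1.644 (+3.1%), and under no effect 1.014 v 0.982 (+3.3%).

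In the no-effect case the groups differ only in censoring, so swapping their labels turns a factor of 1.033 into 1/1.033 = 0.968. The direction is not fixed.

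**6. The planned comparison.** Excluding children who die or are transplanted conditions on a future outcome. For a true 60% it gives roughly 0.60/0.90 = 67% at 10% death or transplant and 0.60/0.80 = 75% at 20%. Simulated values run from 66% to 85% over 10% to 30%. It errs upward and cannot show or correct the downward bias.

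**The case against.** The other side has a good case on size. The device is reasoned, aims at the right quantity and is exact without early censoring. It is far better than censoring the deaths, which would give about 64% to 78% for a true 60%. The Missing Values section expects nearly complete data, the study is open-ended with yearly safety-board meetings, and children stay on treatment until weaned from parenteral nutrition. Censoring concentrated in the first 12 months is therefore not what the documents suggest. Sampling error dwarfs the bias, root-mean-square error barely changes, and the protocol calls the result preliminary evidence.

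Most of that stands as a limit on size, but it does not remove the defect. The data expectation concerns missing laboratory values rather than children still un-normalised at closure. An open-ended study closed from outside can still censor recent entrants early. The bias is also systematic, whereas the SD is not.

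A reader might infer three stronger claims, none of which is supported:

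- That the curve is understated by several points as a matter of course. No rate is stated, and moderate assumptions do not give this.
- That Greenwood standard errors become materially too narrow. In the n = 30 case they were 0.106 against an actual SD of about 0.109 to 0.110 at 9 months.
- That every hazard ratio is pushed against Omegaven. The shift is small and varies in direction.

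**Conclusion.** The point holds as a modest technical defect. With early censoring of living children, which the protocol permits, the stated method biases the Kaplan-Meier normalisation probability downward. On assumed rates this is about 0.2 to 2 points under moderate censoring, with one timing pattern reaching 2.6. It is 3 to 6 points only under heavy censoring or early, frequent death or transplant. With no early censoring it is zero. The effect on Cox hazard ratios is about 2 to 3% with no fixed direction. The mechanism and the direction for the curve do not depend on the assumed rates; every size does. The finding does not show that the trial's conclusion would change.

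**What to change.** Keep the estimand and change the estimator in Analysis of Efficacy of Omegaven®.

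- **Curve:** report the Aalen-Johansen cumulative incidence of normalisation, with death or liver transplant as a competing event. Do the same for time to a total bilirubin of 1.2.
- **Regression:** use a Fine-Gray model in place of Cox with infinite times. Alternatively, keep a child who died or was transplanted in the risk set only until that child's potential end of follow-up. That date is known where censoring is purely administrative; where loss or withdrawal also occurs, the Fine-Gray weights handle it.
- **Comparison analysis:** do not rely on the exclusion analysis as the check on this handling.

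The cost is a minor change of wording and standard software, with no new data beyond event and follow-up dates. Variance is slightly larger at this sample size, with similar overall error at n = 30. If no child is censored early, the new curve equals the current one.
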